- Some subjects may not receive clinical benefit from eCoin therapy in either arm; however, the expectation is that subjects will continue with the trial, at least until the primary endpoint, regardless of response. Some individuals who initially do not receive clinical benefit may benefit from late response and cumulative effects of treatment.
- At unblinding, subjects will be offered reprogramming if desired.
- Subjects are intended to be without pharmacological medications for overactive bladder. If the addition of medications is medically necessary as described herein, such information will be collected and reported.

2-4 Study Procedures

All subjects will be followed for up to 4 months post-activation. A 3-day voiding diary will be collected that reports the number and type of incontinence episodes. Subjects will be administered questionnaires including the OABq and patient satisfaction surveys at 2, 3, and 4 months post-activation.

The follow-up study visits are described in relationship to the initial activation visit occurring about 4 weeks after implantation of the study device. See Visit Overview 2-4-2 for exact timing of such visits. For any enrolled subject who is not activated, the same schedule will be followed as if the subject were activated.

Subjects should avoid concomitant therapies, including OAB medications, onabotulinumtoxinA, PTNS or TENS therapies, until the primary endpoint at 3 months. If taken, these therapies will be recorded and noted in the results. Subjects who are taking pharmacologic medication at screening should be washed off OAB medications for a period of 2 weeks prior to filling out the baseline diary.

All subjects will exit from the study after the last study visit at 4 months post activation. Patients may retain their device and remain under the care of their implanting physician.

COVID-19 Considerations

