Subjects will be followed up in visits at 2, 3 and 4 months post-activation, with the primary analysis at 3 months.

- 1) Overactive bladder medications should be avoided, especially prior to the primary endpoint at 3 months. Any medications taken throughout the study should be noted as soon as they are added to the subject's treatment.

- 2) At least 3 days prior to each appointment, subjects will be responsible to complete a 3-day voiding diary to be brought with them to each appointment.
- 3) All other visits are also described in the Visit Overview Section 2-4-2.

If a subject is explanted for any reason they may choose to remain in the study (e.g. continue to attend visits) if they wish.

2-4-12 Plans to Minimize Loss to Follow-Up

Plans to minimize loss to follow-up include:

- Trial design and management that limits the patients' burden and inconvenience during the collection phase including: minimal number of visits and assessments, short study timeline, user friendly diary collection methods, and allowing a relatively large time window for each follow-up
- Training of the site staff to emphasize the importance of the informed consent process as a mechanism for ensuring that participants understand the commitment they are making, including their intent to complete the trial regardless of the treatment they are receiving. Training of investigators and research staff should also emphasize how to work with participants to minimize the extent of missing data.
- Regular and thorough monitoring of the trial data, identification of poorly performing sites in order to implement some form of remediation, including additional training, site visits, or even site closure.

2-4-13 Subject Compliance Monitoring

eCoin Therapy: Neurostimulation therapy is provided automatically by the implant system and has no compliance requirements.

Data: Compliance with voiding diaries is established through review by the clinical study coordinator at each center.

Appointment Compliance: Clinics' designated study coordinators will ensure subjects are compliant with study appointments within the scheduling parameters outlined in the Visit Overview described in Section 2-4-2.

2-5 Safety and Adverse Events

2-5-1 Definitions of Adverse Events

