Subjects may voluntarily withdraw from the study for any reason at any time. They may be considered withdrawn if they state an intention to withdraw, fail to return for visits, or become lost to follow-up for any reason. Any subject considered withdrawn will be exited from the study.

2-5-3-2 Terminating Subject Participation

A subject's continued participation in the study must be terminated if in the Investigator's opinion, continued participation would be detrimental to the subject's well-being. If the subject is unwilling or unable to attend all remaining follow-up visits, or if subject is lost to follow-up, the subject's continued participation must be terminated.

2-5-3-3 Withdrawal/Termination Procedures

If premature withdrawal occurs for any reason, the Investigator must make every effort to determine the primary reason for a subject's premature withdrawal from the study and record this information on the CRF for reporting to the Sponsor.

Subjects enrolled in the study will not be replaced if they withdraw or are terminated from the study after randomization.

2-5-3-4 Early Study Termination

The study can be terminated at any time for any reason by Valencia Technologies. Should this be necessary, the subjects should be seen as soon as possible and treated as described in the early withdrawal section for a prematurely withdrawn subject. The Investigator may be informed of additional procedures to be followed in order to ensure that adequate consideration is given to the protection of the subjects' interests. The Investigator will be responsible for informing the IRB of the early termination of the trial.

2-5-3-5 Data Collection and Follow-up for Withdrawn Subjects

Subjects who are not implanted with the eCoin study device will not be followed after termination or withdrawal from the study.

2-6 Data Analysis Plan

2-6-1 Data Collection

All study data will be recorded onto Case Report Forms (CRFs) provided by the sponsor. All CRFs will be completed using de-identified data. Valencia will enter the recorded data into a database.

Case Report Forms (CRFs): Data will be entered in the CRFs at the Study site. Trained study personnel will be responsible for entering data on the observations, tests, and assessments specified in the protocol onto the CRFs and according to the CRF instructions and sending the CRFs to the designated sponsor representative in a timely fashion.

CRFs for the study include:

- 1) Screening
- 2) Baseline
- 3) Implantation

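### Protocol 2-5-3-2 can force termination, before the month-3 visit, of a subject whose primary data could still be obtained

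*Protocol*

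**What the plan says.** **Exit rules.** Protocol 2-5-3-2 sets the trigger, "If the subject is unwilling or unable to attend all remaining follow-up visits, or if subject is lost to follow-up", and the consequence: "the subject's continued participation must be terminated". Section 2-5-3-1 adds a discretionary route: "They may be considered withdrawn if they state an intention to withdraw, fail to return for visits, or become lost to follow-up for any reason". It gives no count of missed visits. Once that decision is taken the result is automatic: "Any subject considered withdrawn will be exited from the study". No final diary or survey at exit is specified. Section 2-5-3-5 limits follow-up after exit only for one group, "Subjects who are not implanted with the eCoin study device will not be followed after termination or withdrawal from the study", and is silent on implanted subjects. Section 2-5-3-3 rules out replacement after randomization.

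**Rules that favour staying in.** Protocol 2-3-4 expects subjects to continue at least to the primary endpoint whatever their response. Section 2-4 says: "For any enrolled subject who is not activated, the same schedule will be followed as if the subject were activated". Section 2-4-11 says: "If a subject is explanted for any reason they may choose to remain in the study". Section 2-4-12 plans training aimed at limiting missing data, and 2-6-7 relies on planning to keep dropout low. Section 2-7-6-2 lists out-of-window visits and unreturned diaries as minor deviations. The COVID-19 text under 2-4 allows remote visits covering all study activities, with the diary and surveys sent in electronically.

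**Handling of missing data.** SAP 8.6.1 drops a subject only from a timepoint at which there are no data. Protocol 2-6-7 and SAP 10.1 rule out imputation of missing outcomes. SAP 10.3 plans no sensitivity analysis for missing data. Protocol 2-6-4-2 and SAP 7.1 and 7.2 make month-3 data a condition of entry to both the per-protocol and the ITT sets.

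**The concern.** The primary result comes from the month-3 diary at Visit 7 (weeks 12 to 14 after activation), but one visit follows it (Visit 8, weeks 16 to 18). A termination rule that looks at all remaining visits can therefore be triggered by a problem with month 4 and cost the month-3 result. Staying in contact with a subject and attending every visit are different things, and the exit sections do not separate them.

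At stake is the completeness of a small randomized comparison. A subject removed before Visit 7 disappears from both effectiveness sets, so the ITT analysis cannot show what the per-protocol analysis lost. If willingness or ability to return is related to benefit or discomfort, and either differs by arm, the subjects left are a selected group. With up to 10 centers and no threshold for missed visits, sites may also apply the discretionary rule differently.

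**Working it through.** **1. The two readings of 2-5-3-2.** Take a subject with working stimulation and intact consent, before Visit 7.

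- *Literal reading: cannot attend every remaining visit.* Someone able to attend month 3 but not month 4, who says so in time, must be terminated. The month-3 diary is then not collected.
- *Softer reading: can attend none of the remaining visits.* That person stays in. A person who cannot come in but could return the diary, OABq and survey is still terminated. The remote route that would capture those data is offered only under the COVID-19 heading.

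Some obtainable month-3 data can be lost on either reading, though less on the second.

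**2. Is the loss repaired later?** No. Replacement, imputation, a missing-data sensitivity analysis and an ITT set that keeps subjects without month-3 data are all absent. One limit on the concern: under SAP 8.6.1, month-3 data already collected survive a later exit. Only exits before Visit 7 matter for the primary result.

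**3. The plan's precision figures.** Inputs from Protocol 2-6-5 and SAP 6: SD 2, two-sided 95% t interval, benchmark mean reduction 1.3, minimum 16 per arm, loss 10% + 2% + 3% = 15%. The formula is D = t(0.975, n−1) × 2 / √n.

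- n = 16: D = 1.0657, stated 1.07; interval 1.3 ± 1.0657 = (0.23, 2.37), as stated.
- 16 × 0.85 = 13.6, taken as 13: D = 1.2086, stated 1.21.

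All eight tabulated rows (n = 13 to 20) reproduce to two decimals.

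**4. Effect of further exits.** The documents give no number of exits caused by these rules, so extra losses per arm beyond the 15% are an assumption, shown as a range. At the target of 40 there are 20 per arm, and 20 × 0.85 = 17.

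| Extra exits per arm | From 20: n left | D | From 16: n left | D |
|---|---|---|---|---|
| 0 | 17 | 1.03 | 13 | 1.21 |
| 1 | 16 | 1.07 | 12 | 2.201 × 2 / 3.464 = 1.27 |
| 2 | 15 | 1.11 | 11 | 2.228 × 2 / 3.317 = 1.34 |
| 3 | 14 | 1.15 | 10 | 1.43 |

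The smallest n with D below 1.3 is 12, so an arm must fall to 11. That is 20 − 11 = 9 losses in total (9/20 = 45%) at the target size, or 16 − 11 = 5 losses (5/16 = 31%) at the stated minimum.

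**5. Scale of a selection effect.** This too is an assumption. If m of 17 evaluable subjects are lost and their mean reduction differs by d from those kept, the observed arm mean is off by (m/17) × d. With d equal to one planning SD (2), this is 1 × 2/17 = 0.12 for one exit and 3 × 2/17 = 0.35 for three.

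**The case against.** The strongest reply is that the sentence in 2-5-3-2 is paired with loss to follow-up and sits in a termination section, so it may well mean a subject who will attend nothing more. Little obtainable data would then be lost. That is a fair reading, and the ambiguity must be conceded. It does not remove the problem, because remote return of data is not open to such a subject outside the COVID-19 text.

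Four stronger inferences are tempting and are not supported.

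- *That missing a visit means exit.* Section 2-5-3-1 is permissive; only the exit after the decision is automatic. The COVID-19 text lists missed visits separately from discontinuations.
- *That month-3 data are discarded.* SAP 8.6.1 keeps what was collected. The risk is that data are never collected.
- *That the protocol contradicts itself.* The passages on non-activated and explanted subjects concern device status, not ability to attend. They are in tension with the exit rules, no more.
- *That the sample size fails.* The 15% allowance already contains 10% dropout, so adding exits on top partly counts the same subjects twice. The 1.3 figure is a planning benchmark, and the SAP states that there are no pass/fail criteria.

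It is also fair to say that a subject who can attend month 3 but not month 4 may simply have a scheduling conflict. Selection is possible, not shown.

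**Conclusion.** The concern holds as one of completeness and possible selection. A mandatory rule, on its literal reading, ends participation before the primary visit for a subject able to attend it. On its softer reading it still ends participation for a subject able to supply the same data remotely. A discretionary rule with no threshold adds to this, and the analysis plan has no way to recover or examine what is lost.

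The size cannot be fixed from the documents, because nothing states how many subjects would be affected. On the assumed range, the effect on precision is small at the planned 20 per arm: 1.03 with no extra exits and 1.15 with three. A reader might infer that the study would miss its precision benchmark. That would need nine losses in an arm of 20, three times the 20 × 0.15 = 3 planned for. The selection illustration rests on an assumed difference of one SD between lost and retained subjects, for which the documents give no evidence. The change is still worth making, because the loss is avoidable and the remedy is cheap.

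**What to change.** Reword Protocol 2-5-3-1 and 2-5-3-2 so that:

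- a consenting subject who misses, or expects to miss, one or more visits stays in the study and is contacted for each remaining visit;
- a missed visit is recorded separately from a withdrawal on the CRF;
- when Visit 7 cannot be attended for any reason, the diary, OABq and satisfaction survey may be returned by the remote route already described under 2-4, no longer limited to COVID-19;
- for a remote Visit 7, unblinding and any reprogramming offer are made only after those assessments have been received, which keeps the order that 2-4-2 already sets.

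Leave the subject's right to withdraw and the investigator's well-being criterion as they stand. The cost is a protocol wording change and some extra reminder calls; no visit is added.

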All subjects will return for a device activation visit approximately four weeks after implantation. At this point, the follow-up visit clock will start to run (that is, the follow-up visits will be characterized in relationship to the date of the activation visit).

The subject will be provided with a 3-day voiding diary to complete in the 7 days prior to the next visits (occurring 2 and 3 months post-activation). At least 3 days prior to the next visit, a member of the study staff will telephone subjects to remind them that they should begin the 3-day diary.

2-4-10 Establishment of the Amplitude Setting in each Treatment Arm

Amplitude level ranges in practice from 0.5 to 15 mA. Sensory threshold is defined as the lowest amplitude where the subject first perceives sensation of the stimulation in the foot, heel, toes or eCoin device site while in a prone, seated and standing position.

Subjects will be informed that they may periodically feel a tingling or notice a muscle twitch. In particular, subjects may feel a motor response (flexing of the big toe and/or fanning of the other toes) and sensory response (a radiating sensation may be felt at the sole of the foot and in the toes). Typical descriptions of tibial nerve stimulation sensation include feeling a 'buzzing', 'tingling' and 'vibrating' sensation.

2-4-10-1 Sensory Treatment Arm Activation Protocol

The subject's sensory threshold is determined by turning the device on to 0.5 mA and increasing the amplitude by one level until the subject reports sensation. If the subject does not feel sensation at any amplitude, they will be set at 8 mA, this will be considered a deviation to the protocol.

2-4-10-2 Subsensory Treatment Arm Activation Protocol

The subject's sensory threshold is determined by turning the device on to 0.5 mA and increasing the amplitude by one level until the subject first reports sensation. Once the first sensory threshold is determined, the set amplitude will be lowered to approximately 75% of the sensory threshold, accounting for rounding. Patients who do not have sensory at the highest amplitude will be set at 11mA. See the below table for sensory threshold and level set correlations:

Sensory Threshold	Level Set
0.5 mA	Protocol Deviation, set 0.5 mA
1 mA	0.5 mA
2 mA	1 mA
3 mA	2 mA
4 mA	3 mA
5 mA	4 mA
6 mA	5 mA
7 mA	5 mA
8 mA	6 mA
9 mA	7 mA
10 mA	8 mA
11 mA	8 mA
12 mA	9 mA
13 mA	10 mA
14 mA	11 mA
15 mA	11 mA
No sensation	11 mA

2-4-11 Post Activation Follow-up Procedure

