The remainder of this section briefly describes the analyses planned for this study. A full Statistical Analysis Plan (SAP) will be prepared. The SAP will include more technical and detailed descriptions of the statistical analyses. If there are minor differences between the analyses described in this section and the analyses in the SAP, the analyses in the SAP will prevail. A change to the data analysis methods described in the protocol will require a protocol amendment only if it alters a principal feature of the protocol.

2-6-4-1 Effectiveness

This randomized, double blinded study will evaluate eCoin's effectiveness reducing episodes of urgency urinary incontinence with programming at sensory and subsensory levels. The reduction in the number of urgency urinary incontinence episodes will be reported at 2 months, 3 months (primary endpoint), and 4 months post-activation.

2-6-4-2 Analysis Sets

The primary analysis will be performed in the Per-Protocol (PP) population, defined as subjects who undergo an implantation procedure, are OAB drug free, and who have data available at the primary endpoint, excluding all major protocol deviations and any significant departures from the amplitude programming protocol (no sensory at any level for sensory arm, and sensory at lowest setting for subsensory arm, reprogramming that is a significant departure from the assigned treatment stimulation, or device not activated).

In addition to the primary analysis, an analysis will be performed of the Intent-to-Treat (ITT) population defined as all subjects who undergo a procedure for implantation of eCoin and who have

data available at the primary endpoint.

Safety data will be reported on all enrolled subjects who undergo a procedure for implantation of the study device. Safety data will be reported for all device related adverse events, procedure related adverse events, and serious adverse events.

The SAP may define additional analysis sets of subjects.

2-6-4-3 Planned Analyses

2-6-4-3-1 Primary Endpoint

1. The primary endpoint is the reduction from baseline in the number of urgency urinary incontinence episodes per day on a 3-day voiding diary (72 hours) after 3 months of eCoin tibial nerve stimulation.

2-6-4-3-2 Secondary Endpoint(s)

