## 7.1. Per Protocol Population

The Per Protocol population will include all subjects in the Intent to Treat population with no major protocol deviations. Subjects in the PP population must remain OAB drug-free for the duration of the study. Additionally, subjects should not have any significant departures from the amplitude programming. This is the primary and secondary endpoint analysis population.

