## 8. General Statistical Conventions and Considerations

Descriptive statistics will summarize results of the ESSENCE protocol. Standard descriptive statistics, such as number of subjects, mean, standard deviation, quartiles, minimum, and maximum, will be calculated for continuous variables. For discrete variables, summary tables will display numbers of subjects and related percentages. Tables will display three columns of results showing all data as well as the sensory and subsensory treatment arms. The general statistical conventions and definitions used for the data analysis are described below.

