## 9.6. Treatment Compliance

The ESSENCE study will explore the effect of sensory and subsensory treatment arms. Significant departures from the assigned amplitude programming protocol include:

- no sensory level identified for the sensory arm
- sensory level identified at the lowest amplitude setting (0.5 mA) for the subsensory arm
- reprogramming visit prior to 3 months that is a significant departure from the assigned treatment stimulation
- device not activated
- device turned off
- A protocol deviation related to device programming does not match assigned treatment arm

Any non-compliances to the assigned treatment arm at randomization will be listed by subject. This listing will include the date of randomization, assigned treatment arm, and reason for departure, and date of treatment noncompliance.

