## 10. Efficacy Analysis

### 10.1. Primary Efficacy Analysis:

This randomized controlled double-blind study will evaluate the efficacy of eCoin in reducing episodes of UUI per day with two different treatment arms. The primary efficacy outcome is the reduction from baseline in the number of UUI episodes per day on a 3-day voiding diary (72 hours) after 3 months of eCoin device tibial nerve stimulation. The voiding diary CRF will report the total over the 3 days for each measure, which will then be averaged.

The primary efficacy analysis will be performed on the Per Protocol population. The change from baseline will be summarized with descriptive statistics (n, mean, median, standard deviation, 25th quartile, 75th quartile, minimum, and maximum). Additionally, the mean reduction of UUI episodes per day along with its two-sided 95% confidence interval will be summarized for all subjects, sensory arm, and subsensory arm. Boxplots and line graphs with observed values and change from baseline may also be presented. Treatment effect size may be reported using Cohen's d and/or relative risk to highlight the observed differences, if any.

No data imputations will be performed for subjects who do not have 3-month post-activation data. Missing and incomplete diary data will be handled per section 8.6.3 Missing or Incomplete Diary.

The primary endpoint is exploratory in nature. There are no pass/fail criteria to define the study success and there is no powered comparison between the two treatment arms

Because this study is exploring the efficacy of the eCoin System programmed using two different methodologies, the per protocol population will be analyzed for the primary endpoint. The per protocol population, as described in section 7. Analysis Populations, will exclude patients that have taken OAB medications, do not meet eligibility criteria, experience major protocol deviations and/or experience departures

from the assigned programming treatment. Due to the nature of the study, it is expected a subset of all implanted subjects will have data on the primary endpoint.

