## 10.3. Sensitivity and Additional Analysis

The primary and secondary efficacy analysis will be repeated the ITT population. There is no planned sensitivity analysis for missing data.

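### The per-protocol set excludes each problem threshold type from one arm only, so a between-arm effect size computed on it compares arms selected by different rules

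*Protocol*

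**What the plan says.** Protocol 2-6-4-2 makes the per-protocol set primary and excludes significant departures from the programming protocol, among them "no sensory at any level for sensory arm, and sensory at lowest setting for subsensory arm". SAP 7.1 carries this over: "Additionally, subjects should not have any significant departures from the amplitude programming". SAP 9.6 lists what counts as a departure, including "no sensory level identified for the sensory arm" and "sensory level identified at the lowest amplitude setting (0.5 mA) for the subsensory arm". SAP 10.1 confirms that departures from the assigned programming leave the primary set.

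The titration is the same in Protocol 2-4-10-1 (sensory) and 2-4-10-2 (subsensory): "The subject's sensory threshold is determined by turning the device on to 0.5 mA and increasing the amplitude by one level". The mirror cases are kept. A subsensory subject with no sensation is set at 11 mA and no deviation is named. No deviation is named for a sensory-arm subject whose threshold is 0.5 mA.

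On output, SAP 8 states: "Tables will display three columns of results showing all data as well as the sensory and subsensory treatment arms". SAP 10.1 gives means with 95% confidence intervals overall and by arm, calls the endpoint exploratory and disclaims any powered comparison. It then adds: "Treatment effect size may be reported using Cohen's d and/or relative risk to highlight the observed differences, if any". SAP 10.3 provides a second look: "The primary and secondary efficacy analysis will be repeated the ITT population". The ITT definition in SAP 7.2 has no threshold rule.

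**The concern.** Threshold is a patient characteristic found before the working amplitude is set, so randomisation should spread both unusual types evenly. The exclusion rule undoes that. The sensory per-protocol set has no no-threshold subjects but keeps those at 0.5 mA; the subsensory set is the reverse. The kept subjects also sit at the extremes of amplitude, which is the variable under study: 0.5 mA in one arm and 11 mA in the other.

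The trial asks how two amplitude settings perform, and the arms are tabulated side by side. An effect size on this set would mix any amplitude effect with the one-sided selection.

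The planned tables do not show the mix. SAP 9.5 and 9.6 reveal the excluded subjects but not the retained mirror cases. SAP 9.7 covers demographics, smoking and OAB history, and SAP 9.8 covers durations.

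**Working it through.** **Inputs (Protocol 2-6-5, SAP 6).** No threshold identified: 6.15% of 130, i.e. 8/130. Threshold 0.5 mA: 3.85% of 130, i.e. 5/130. Dropout 10%. SD 2, two-sided 0.05. Planned 40 subjects (20 per arm), maximum 50, stated minimum 16 per arm.

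**The plan's own figures.** Precision is D = t(0.975, n−1) × 2/√n. This gives 1.07 at n = 16 and 1.21 at n = 13, and all eight rows of the table reproduce. The 15% loss is 6.15%/2 + 3.85%/2 + 10% = 15.0%. The halving shows that the plan itself counts each exclusion in one arm only. Then 16 × 0.85 = 13.6, which the plan takes as 13.

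**Expected imbalance at 20 per arm, before dropout.**
- No-threshold: 20 × 0.0615 = 1.23, dropped from sensory and kept in subsensory.
- 0.5 mA threshold: 20 × 0.0385 = 0.77, dropped from subsensory and kept in sensory.
- Chance that at least one one-sided subject is kept: 1 − (0.9385 × 0.9615)^20 = 0.87. With 16 per arm it is 0.81.

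**Shares of the per-protocol set.** These assume equal rates in both arms and dropout unrelated to threshold.
- Sensory, 0.5 mA: a = 0.0385/(1 − 0.0615) = 0.041.
- Subsensory, no threshold: b = 0.0615/(1 − 0.0385) = 0.064.

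**Shift in the between-arm difference.** Suppose there is no amplitude effect and other subjects have mean reduction M. Let the 0.5 mA type have M + dL and the no-threshold type M + d0. The sensory mean is M + a·dL and the subsensory mean is M + b·d0, so the difference is a·dL − b·d0. No document gives dL or d0. Assume each has absolute size 1 to 2 episodes/day.
- Same direction: the minimum is 0 (when dL/d0 = 0.064/0.041 = 1.56). The maximum is |0.041 × 1 − 0.064 × 2| = 0.087.
- Opposite directions: 0.041 + 0.064 = 0.105, up to 2 × 0.105 = 0.21.
- Wider assumption, gaps up to the pivotal 8-week mean reduction of 2.3: at most 2.3 × 0.105 = 0.24.

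**Against sampling error.** The plan leaves on average 20 × 0.85 = 17 per arm. The half-width for a difference is t(0.975, 32) × 2 × √(2/17) = 1.40. So 0.21 is 0.21/1.40 = 15% of the half-width, or 0.21/2 = about 0.1 SD.

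**Size of a symmetric set.** Excluding both types from both arms leaves n × (1 − 0.10 − 0.0615 − 0.0385) = 0.80n.

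| Per arm enrolled | Left per arm | One-arm precision |
|---|---|---|
| 16 | 12.8 | 1.27 (n = 12) to 1.21 (n = 13) |
| 20 | 16.0 | 1.07 |
| 25 | 20.0 | 0.94 |

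At 16 per arm analysed, the half-width for a difference is t(0.975, 30) × 2 × √(2/16) = 1.44.

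**The case against.** The strongest reply is that the plan does not rest on the comparison. Its primary output is a mean and interval within each arm, it repeatedly disclaims a powered comparison, and the effect size is optional. For a within-arm estimate each rule makes sense: a sensory setting cannot be delivered without a threshold, and a subsensory setting cannot be delivered below the lowest level. This stands. A reader might infer that the primary analysis itself is biased, and the documents do not support that.

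Second, a check is already planned, since the ITT repeat keeps both types in both arms. This stands in part. ITT also readmits drug users, major deviations and reprogrammed subjects, so a change between the two sets could not be traced to threshold selection.

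Third, the excluded subjects are not hidden. SAP 9.1 counts both sets by arm, SAP 9.5 tabulates deviations by reason and SAP 9.6 lists each departure. This is correct, and only the retained mirror cases go unreported.

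Fourth, the size rests on an assumed outcome gap, and the 87% is only the chance that such a subject is present. A reader might infer that the rule could create or hide a treatment difference. Under the assumed range the shift is far inside sampling error.

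Finally, a symmetric set is not fully balanced, because exclusions for drug use or for reprogramming after discomfort may also differ by arm. This stands and limits what the sensitivity summary can claim.

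**Conclusion.** The asymmetry is explicit in both documents and affects any between-arm effect size computed on the per-protocol set. It does not invalidate the within-arm primary summaries. The expected imbalance is about one subject per arm of 20. The shift is 0 to 0.21 episodes/day, at most about 15% of the half-width of 1.40. It rests on the pivotal rates holding equally in both arms, an SD of 2, dropout unrelated to threshold, and an assumed gap of 1 to 2 episodes/day for each type. This is a low-priority improvement, worth making because the titration already yields the data needed.

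**What to change.** Keep the current per-protocol set for the primary within-arm summaries. Then:

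- **SAP 10.3:** add a sensitivity summary of the primary outcome in per-protocol subjects, after excluding from both arms those with no sensory threshold identified and those with a threshold of 0.5 mA.
- **SAP 10.1:** if a between-arm effect size is reported, give it in this symmetric set as well, with that set's own arm means, beside the per-protocol value and not in place of it.
- **SAP 9.1 or 9.7:** tabulate the number of subjects of each threshold type by randomised arm.

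The cost is SAP wording, one table and two count rows. Protocol 2-6-4-2 already lets the SAP define further analysis sets. The change should precede database lock, because SAP 8.4 labels later changes exploratory.

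The symmetric set loses about one subject per arm (16 against 17 of 20): one-arm precision is 1.07 against 1.03, and the half-width for a difference is 1.44 against 1.40. At the stated minimum of 16 per arm, precision is 1.21 to 1.27, still below the plan's assumed effect of 1.3. The set omits some subjects treated as assigned and leaves the other post-randomisation exclusions in place, so it should be described as removing this one imbalance only.
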